Safety is an important first step and study outcome. In the published phase 2 and 3 studies of solriamfetol in patients with narcolepsy or obstructive sleep apnea (OSA), adverse events included headache (9-16%), nausea (12-14%), diarrhea (11%), decreased appetite (6-14%), anxiety (6-11%), chest discomfort (9%), insomnia (6%), muscle tightness (6%), nasopharyngitis (5-14%), and dry mouth (5-10%). Cancer patients and in particular brain tumor patients are at risk for some of these and other cognitive, seizure, or neurological toxicities that need to be explored at each of solriamfetol's three dose levels (75 mg, 150 mg, 300 mg) prior to proceeding to a primary efficacy endpoint. The current trial will establish this experience.

Prior studies of solriamfetol have shown early improvements in patient-reported sleep by ESS scores. In the current study we will also evaluate other associated symptoms of fatigue, neurocognition, mood, and quality of life. It is not clear that these associated symptoms will respond as quickly to drug therapy. In fact, according to our model of the sleep-fatigue-neurocognitive symptom cluster (Figure 1), we suspect that improvement in fatigue, neurocognition, mood and quality of life are downstream of the improvement in sleep and thus, in this study, endpoints will be assessed after prolonged stable drug therapy. This should not affect the ability to assess for improvements in sleep which have been reported as early as 1 week after solriamfetol treatment and remained stable over up to 12 weeks of continued treatment in the aforementioned studies.

2 Hypotheses

1. Primary Hypothesis

We hypothesize that the side effect profile of solriamfetol at doses of 75 mg daily, 150 mg daily, and 300 mg daily will be similar in patients with primary brain tumors to that reported in patients with narcolepsy and obstructive sleep apnea.

Serious adverse events in patients with primary brain tumors including significant confusion/ altered mental status, seizures, or other side effects will not be more common at the 300 mg daily dose compared to the 150 mg and 75 mg daily doses.

2. Secondary Hypotheses

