Secondary hypotheses include that solriamfetol treatment at maximal patient specific dosing will result in improvements in patient-reported excessive daytime sleepiness and sleep quality (e.g. ESS and PSQI), neurocognitive function (see below for neurocognitive battery), fatigue and mood (e.g. Brief Fatigue Inventory, Cancer Fatigue Scale, Beck Depression Inventory), and quality of life (FACT-Brain).

3. Exploratory Hypotheses

Improvements in objective measures of sleep (e.g. actigraphy, sleep diary) will be similar to those reported in prior studies (e.g. obstructive sleep apnea, narcolepsy). We hypothesize that improvements in sleep, neurocognition, fatigue, mood, and quality of life may vary by clinical factors such as corticosteroid use, antiepileptic use, and tumor grade by World Health Organization (WHO) classification.

3 Objectives

1. Primary Objective(s)

1. To estimate the safety of solriamfetol at 75 mg daily, 150 mg daily, 300 mg daily as assessed by NCI CTC Adverse Events (v5.0) in patients with primary gliomas compared to prior studies⁴⁵⁻⁴⁷

2. Secondary Objective(s)

1. To estimate the effect of solriamfetol on sleep by Epworth Sleepiness Scores (ESS) scores in patients with primary gliomas and compare the effect to previously published scores in patients with OSA
2. To estimate the effect of solriamfetol on sleep quality by Pittsburgh Sleep Quality Index scores
3. To estimate the effect of solriamfetol on neurocognitive function based on a disease-specific neurocognitive battery (see neurocognitive battery below)
4. To estimate the effect of solriamfetol on patient-reported fatigue (Brief Fatigue Inventory, Cancer Fatigue Scale) & mood (Beck's Depression Inventory)
5. To estimate the effect of solriamfetol on patient-reported QOL (FACT-Br)
6. To estimate the effect of solriamfetol on objective sleep-wake times by actigraphy and sleep diary (pre- vs post-treatment)

3. Exploratory Objective(s)

1. To explore a biologic gradient effect of increasing doses of solriamfetol on actigraphy
2. To explore differences in clinical activity of solriamfetol by corticosteroid use, antiepileptic use, and tumor grade

4 Patient Selection

Inclusion and exclusion criteria represent standard criteria for other sleep studies in this population (e.g. inclusion criteria) and standard exclusions for prior studies of this agent (e.g. exclusion criteria).^{8,39,40}

1. Inclusion Criteria

1. WHO Grade 2-4 infiltrating glioma by histologic confirmation

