Storage Requirements: solriamfetol tablets are to be stored at room-temperature conditions, 15°C to 30°C (59°F to 86°F).

Stability: Studies are ongoing to monitor the stability of solriamfetol tablets.

12 Data Management

Informed consent document	EPIC
Protocol registration form	OnCore
Adverse Events Log (Appendix E)	OnCore
Patient Drug Diary (Appendix F)	
Fixed Dose Patient Drug Diary (Appendix G)	
Epworth Sleepiness Scale (Appendix H)	
Pittsburgh Sleep Quality Index (Appendix I)	
Brief Fatigue Inventory (Appendix J)	
Cancer Fatigue Scale (Appendix K)	
Beck's Depression Inventory (Appendix L)	
Neurocognitive Battery Form (Appendix M)	
FACT-Br (Appendix N)	
Concurrent Medication (Appendix O)	OnCore
Off-Study Form (Appendix P)	OnCore
MR Imaging Record (Appendix Q)	
Sleep Diary and Actigraphy Record (Appendix R)	
Glioma History (Appendix S)	

13 Statistical Considerations

This is a single-arm, open label, non-randomized safety study in patients with stable glioma disease. The primary outcome is safety of oral solriamfetol as doses of 75 mg daily, 150 mg daily and 300 mg daily. Secondary outcomes include ESS score, PSQI score, a composite neurocognitive battery score, FSS score, BDI score, and FACT-Br score.

1. Analysis of Primary Objective

For the primary outcome, NCI Common Terminology Criteria for Adverse Events (CTCAE) version 5.0 will be used for scoring toxicity and adverse events.

The severity and frequency of toxicity and adverse events for each dose of solriamfetol will be tabulated using descriptive statistics. The proportions of subjects who experienced grade 3 or above toxicities will be estimated, along with 95% confidence intervals by each type of toxicity.

To compare the safety of solriamfetol at 75 mg daily, 150 mg daily, 300 mg daily, chi-squared statistics will be used. If there are some cells with expected value <5 , Fisher's exact test will be used for the comparison.

2. Analysis of Secondary Objective

For the secondary outcomes, descriptive statistics will be performed for each of the outcome measures. Changes in pre- and post-treatment scores will be assessed and compared using the pair-t tests if the changes follow a normal distribution and using the Wilcoxon signed rank tests if the changes do not follow a normal distribution. For the comparison between the change in ESS score in the study patients and the published change score in patients with obstructive sleep apnea, we will use the one sample t-test for this comparison.

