3. Analysis of Exploratory Objective

13.3.1 To explore the dose response effect of solriamfetol on actigraphy, linear regression models will be used where the dosage will be treated as an ordinal variable.

Transformation of actigraphy will be performed to satisfy the normality assumption if needed.

13.3.2 The analysis will be the same as that specified in 13.1.

4. Power and Sample Size

We plan to recruit around 36 participants.

In the prior phase 2a and phase 2b studies in patients with narcolepsy which had similar sample sizes, no patients in the phase 2a and three patients in the phase 2b study required discontinuation of study medication, though two of these discontinuations were not attributed to the study drug.^{46,47} In the prior phase 3 study, 9 patients (9%) including one in the 75 mg arm, 3 in the 150 mg arm, and 5 in the 300 mg arm required discontinuation due to treatment related AEs.⁴⁵ In the current study, 36 patients will receive 75 mg daily dosing. We conservatively estimate that at least 33 patients will escalate to 150 mg daily, and at least 30 patients will escalate to receive 300 mg daily. These estimates are felt to be overly conservative based on data from these prior studies in patients narcolepsy.

From prior studies, the most common adverse event proportions range from 10% to 20%. Assuming 10% and 20% of adverse event proportion, the detectable proportions for the combined dosage are 24% and 36%, respectively, in order to reach 80% power at a significance level of 0.1 (given the pilot nature of this study) and a two-sided test. These detectable proportions are reasonable. If we observe an adverse event proportion in the patients with primary gliomas that is higher than 36%, then the adverse event proportion is significantly higher than the other study populations. In practice, if an adverse event proportion is higher than 50%, then the safety/tolerability of solriamfetol needs to be questioned. We should have enough power for this primary analysis. Note that this study allows us to determine safety profiles for the 3 doses of solriamfetol. It is primarily for descriptive purpose and to generate data on safety and estimation of effect size for the design of a subsequent randomized study powered to determine drug activity. The results generated from this study will be beneficial for the future research study.

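### The primary hypothesis of a similar side-effect profile has no similarity criterion, and the one formal comparison with the reference populations, a difference test in 36 patients, cannot support it

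*Combined protocol and SAP*

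**What the plan says.** Section 2.1 (Primary Hypothesis) states that the side-effect profile at the three doses "will be similar in patients with primary brain tumors to that reported in patients with narcolepsy and obstructive sleep apnea". A second statement there, that serious events "will not be more common at the 300 mg daily dose compared to the 150 mg and 75 mg daily doses", compares doses rather than populations and is not the subject of this point.

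The primary objective (3.1) is worded as estimation: "To estimate the safety of solriamfetol at 75 mg daily, 150 mg daily, 300 mg daily as assessed by NCI CTC Adverse Events", set against prior studies.

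Section 13.1 (Analysis of Primary Objective) has three elements:
- "The severity and frequency of toxicity and adverse events for each dose of solriamfetol will be tabulated using descriptive statistics".
- 95% confidence intervals, for grade 3 or higher toxicities only.
- Chi-squared or Fisher tests between doses.

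It names no comparison with other populations.

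That comparison appears in 13.4 (Power and Sample Size). Reference rates of 10% and 20% are assumed, and the detectable all-dose rates are given as 24% and 36% "in order to reach 80% power at a significance level of 0.1 (given the pilot nature of this study) and a two-sided test". A rate above 36% is read thus: "then the adverse event proportion is significantly higher than the other study populations". Section 13.4 also says that a rate above 50% would call tolerability into question, and it describes the study as mainly descriptive.

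**The concern.** A hypothesis of similarity needs either a criterion for what counts as similar or no formal conclusion at all. The plan has neither. A test whose null hypothesis is equality can reject similarity, but failing to reject in a small sample shows little, because large true differences often go undetected.

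The intervals that could inform the question are planned for the wrong events. The reference data in 10.1 are overall subject incidences of headache, nausea, dry mouth and the like, with no restriction by grade, whereas 13.1 gives intervals for grade 3 and above.

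At stake is what the trial may conclude. Section 1.6 says brain tumor patients are at risk of cognitive, seizure and neurological toxicity, and 13.4 says the results will feed a later randomized study. A conclusion of similar safety carried forward without support would matter.

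**Working it through.** **Inputs (13.4).** n = 36; reference rates p0 = 10% and 20%, treated as fixed; alpha 0.10, two-sided; detectable rates 24% and 36% at 80% power. Each patient is counted once over all doses.

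**1. The plan's own figure.** Normal approximation, two-sided 0.10: critical rate = p0 + 1.645 × √(p0(1 − p0)/36), and power at p = Φ[(p − critical rate)/√(p(1 − p)/36)].
- p0 = 10%: critical rate 0.10 + 1.645 × 0.0500 = 0.182; power at 24% = Φ(0.058/0.0712) = Φ(0.81) = 79.1%. This reproduces the plan.
- p0 = 20%: critical rate 0.20 + 1.645 × 0.0667 = 0.310; power at 36% = Φ(0.0503/0.0800) = Φ(0.63) = 73.5%. This does not reproduce 80%.

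A one-sided 0.10 exact test gives 79.5% and 80.2%, so it matches both. That discrepancy is a separate matter. It is relevant here because the plan does not say which version of the test will be used, so results are shown for more than one.

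**2. What counts as non-significant.** Exact binomial, at most 0.05 per tail.
- p0 = 10%: P(X ≥ 8) = 0.024 and P(X ≥ 7) = 0.063, so the test rejects upward at 8 or more. It rejects downward only at 0.
- p0 = 20%: P(X ≥ 12) = 0.042 and P(X ≥ 11) = 0.089, so the test rejects upward at 12 or more. It rejects downward at 2 or fewer.

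The one-sided 0.10 exact test rejects at 7 or more and at 11 or more.

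**3. What the largest non-significant results still allow.** Exact (Clopper-Pearson) 90% upper limit = 0.95 quantile of Beta(x + 1, 36 − x).
- Against 10%: 7/36 = 19.4%, upper limit 33.4%.
- Against 20%: 11/36 = 30.6%, upper limit 45.5%.

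**4. Chance of a non-significant result when there is a true excess.** This is the probability that X falls outside the rejection region at the true rate.

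| Reference | True rate | Exact two-sided | Normal two-sided | Exact one-sided 0.10 |
|---|---|---|---|---|
| 10% | 20% | 57% | 39% | 40% |
| 10% | 24% | 34% | 21% | 20% |
| 20% | 30% | 61% | 55% | 47% |
| 20% | 36% | 31% | 26% | 20% |

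**5. Could 24% and 36% serve as margins?** They are set by the sample size, not by a judgement of what excess is tolerable. Against 10%, a margin of 24% is 2.4 times the reference. A rule requiring the 90% upper limit to lie below 24% allows at most 4/36 (upper limit 23.6%), and a true 15% would still pass 35% of the time (P(X ≤ 4) = 0.355). Diarrhea, dry mouth, insomnia and anxiety, listed at 5% to 8% in 10.1, would have no margin.

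**6. Which reference?** Section 2.1 names narcolepsy and OSA; 7.1 says AE data will be compared with narcolepsy. The AE table in 10.1 gives headache as 46/220 (21%) in narcolepsy and 38/353 (11%) in OSA, so the choice can change the reading.

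**The case against.** The strongest reply is that the plan never says a non-significant result will be taken as similarity. A reader might infer that it would, but 13.4 interprets results in one direction only: high rates are significant or call tolerability into question. The objective is to estimate, and the study calls itself primarily descriptive. This stands, and the point should not be put as a statement of what the sponsor will do.

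A reader might also say that the difference test is the only planned inference. It is not: 13.1 has grade 3 or higher intervals and between-dose tests, and 13.4 has the 50% threshold. It is the only formal comparison of AE rates with the reference populations, and even that appears in the sample-size text rather than in the analysis section.

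It is tempting to say that an excess of the size planned for would be missed one time in three. That holds only for the exact two-sided test; across versions of the test the figure is about 20% to 34%, and 20% is simply what 80% power means. Nor is it a strong argument that losing patients makes a finding of similarity easier: screen failures and patients who take no dose are replaced (7.3, 7.13), which holds the all-dose denominator near 36.

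What survives is that a hypothesis of similarity and a descriptive purpose do not fit together without a criterion, and none is given.

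**Conclusion.** The concern holds in limited form. The stated analysis can contradict the first primary hypothesis but cannot support it, and the plan offers no other route to a conclusion on it. At n = 36, observed rates up to 19.4% (against 10%) or 30.6% (against 20%) are non-significant by the exact two-sided test, with upper limits of 33.4% and 45.5%. Over the tests considered, a true doubling from 10% is non-significant 39% to 57% of the time, and a true 30% against 20% is non-significant 47% to 61% of the time.

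These figures assume a fixed reference rate, 36 evaluable patients and one count per patient. They do not show that a false claim of similarity will be made; they show that non-significance would be poor grounds for one. The correction is worth making because it settles in advance what the trial may conclude.

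**What to change.** 1. In 2.1, replace the similarity statement with an estimation aim that matches objective 3.1: to estimate the frequency of common AEs in glioma patients and describe it beside published rates.
2. In 13.1, add an exact 90% confidence interval for the all-dose proportion of each common AE of any grade, each patient counted once, shown beside the reference rate. The 90% level matches the 0.10 alpha in 13.4.
3. Name the reference population and source for each AE, and reconcile 2.1 with 7.1.
4. State in 13.1 that a non-significant difference from the reference will not be reported as a similar profile.

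If the sponsor prefers to keep a similarity claim, the margin must be chosen and justified for each AE as the sponsor's own assumption. The rates of 24% and 36% are detectable differences and should not be used as margins by default.

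The cost is a wording change and one more interval per common AE, with no extra patients or data. The drawback is a weaker conclusion: the report could describe the AE rates and their uncertainty, but could not claim that the profile is similar.

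### The no-increase hypothesis for serious events at 300 mg is paired only with an unpaired test of difference, and no interval for the dose difference is planned

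*Combined protocol and SAP*

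**What the plan says.** Section 2.1 (Primary Hypothesis) puts forward that serious adverse events, with confusion or altered mental status and seizures named, "will not be more common at the 300 mg daily dose compared to the 150 mg and 75 mg daily doses". No margin is given. The introduction to section 6 also describes the primary objective as a comparison of safety at the three doses, while section 3.1 speaks of estimating safety.

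The matching analysis is in section 13.1: "To compare the safety of solriamfetol at 75 mg daily, 150 mg daily, 300 mg daily, chi-squared statistics will be used". Where an expected cell count is below 5, Fisher's "exact test will be used for the comparison". No significance level, sidedness or event set is stated for this test. The same section tabulates severity and frequency by dose and adds: "The proportions of subjects who experienced grade 3 or above toxicities will be estimated, along with 95% confidence intervals by each type of toxicity".

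Section 7.1 has every patient start at 75 mg and move up weekly to 150 mg and 300 mg unless stopped by toxicity, so the three dose groups are largely the same people. Section 13.4 gives the expected numbers: "In the current study, 36 patients will receive 75 mg daily dosing", and "at least 33 patients will escalate to 150 mg daily, and at least 30 patients will escalate to receive 300 mg daily". Its power statement concerns a different comparison, all doses combined against assumed rates from other populations: "Assuming 10% and 20% of adverse event proportion, the detectable proportions for the combined dosage are 24% and 36%, respectively". Those figures are stated for 80% power with a two-sided level of 0.1. Section 13.4 also calls the study mainly descriptive.

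**The concern.** A hypothesis of no increase needs an analysis that bounds the increase. A test of difference does not do that. When it fails to reject, the data may be compatible with no increase, with a large one, or with both, and only an interval for the difference tells these apart. The intervals that are planned are for single grade 3 or higher proportions by toxicity type. They are not for a difference between doses, and grade 3 or higher is not the same as serious.

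The test also assumes independent groups, which the escalation design does not provide. What is at stake is the reading of the highest dose in a population that section 1.6 describes as at risk of seizures and sensitive to psychoactive drugs, in a study meant to inform a later randomized trial.

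**Working it through.** **Plan's own figure.** Section 13.4 states 24% and 36% as detectable against 10% and 20%. With n = 36 and a one-sample exact binomial rule:
- Against 10%: reject at 7 or more events. P(X ≥ 7 | 0.10) = 6.3% and P(X ≥ 7 | 0.24) = 79.5%.
- Against 20%: reject at 11 or more events. P(X ≥ 11 | 0.20) = 8.9% and P(X ≥ 11 | 0.36) = 80.2%.

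Both figures are recovered, the second only with an upper-tail 0.10 rule. An exact two-sided 0.10 test starts at 12 events there and has 68.9% power. None of this concerns the comparison between doses, for which the plan gives no power.

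**Inputs for the dose comparison.**
- 36 patients at 75 mg and 30 at 300 mg (section 13.4).
- A level of 0.10, two-sided, borrowed from the combined-dose statement. This is an assumption; 0.05 is shown beside it.
- 4.2%: the only overall serious-event rate in the documents (section 10.1, a long-term study in narcolepsy and sleep apnea). Applying it here is an assumption.
- 10% vs 24% and 20% vs 36%: the plan's own pairs, which are rates of common rather than serious events.
- 3% vs 15% and 5% vs 20%: assumed, to show four- to five-fold rises.

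**Formula.** Power = Σ over x, y of Bin(x; 36, p₇₅) · Bin(y; 30, p₃₀₀), summed over tables with Fisher p ≤ α, groups treated as unpaired as in section 13.1.

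| 75 mg vs 300 mg | α = 0.10 | α = 0.05 |
|---|---|---|
| 4.2% vs 8.4% | 14% | 6.5% |
| 4.2% vs 12.6% | 29% | 18% |
| 10% vs 24% | 39% | 27% |
| 20% vs 36% | 37% | 25% |
| 3% vs 15% | 50% | 35% |
| 5% vs 20% | 53% | 40% |

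At 20% vs 36% the expected counts exceed 5 (pooled rate (7.2 + 10.8)/66 = 27.3%; 30 × 0.273 = 8.2), so the plan would use chi-squared. Its power at 0.10 is 42%, and 46% for 10% vs 24%. The picture is unchanged.

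**An example table.** One patient with a serious event of 36 at 75 mg and four of 30 at 300 mg is an observed ratio of (4/30)/(1/36) = 4.8. Fisher's p is 0.17.

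**Allowing for pairing.** An exact McNemar test on 30 pairs, with assumed within-patient correlation of 0 to 0.5 and α of 0.05 or 0.10, has 18% to 43% power for the plan's two pairs and under 4% for 4.2% vs 8.4%. The asymptotic version reaches 68% in its most favourable case.

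**What an interval would show.** With 1/36 and 1/30 observed, the unpaired 90% Newcombe interval for the difference runs from −8.6 to +11.1 percentage points. With no events in 30, the one-sided 95% upper limit for the rate is 1 − 0.05^(1/30) = 9.5%.

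**Would a formal no-increase test do better?** Assume 4.2% at both doses, a 10-point margin (not in the documents) and one-sided 0.05. Approximate power is Φ(0.10/√(0.042 × 0.958 × (1/36 + 1/30)) − 1.645) = Φ(0.37) = 65%. An interval without a pass/fail rule suits this sample size better.

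**The case against.** A reader might infer that the plan will declare 300 mg safe whenever the dose test is non-significant. The documents do not support that. No section says so, and section 13.1 does not tie the test to the serious-event hypothesis. The only interpretive thresholds, in section 13.4, are adverse event proportions above 36% (higher than in other populations) and above 50% (tolerability in question).

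A reader might also infer that a non-significant result is to be expected after any several-fold rise. That goes too far: at four- to five-fold rises from 3% to 5% it is about a coin toss at the 0.10 level.

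The defence can add that the study is described as mainly descriptive, that events are tabulated by dose with some confidence intervals, and that individual serious events are handled by the dose-limiting toxicity rules, safety committee review and an interim safety analysis. All of this stands and limits the consequences. It does not supply the missing quantity, an estimate of the dose difference with its uncertainty, and a descriptive aim favours an interval over a test.

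Finally, a paired analysis has its own bias. Patients stopped by toxicity at a lower dose never form a pair, and most patients spend 7 days at 75 mg but about 7 weeks at 300 mg (one titration week plus six fixed-dose weeks). That objection is sound, and the analysis set and window must be named.

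**Conclusion.** The mismatch is real and visible in the text: a no-increase hypothesis, an unpaired test of difference on largely the same patients, and no interval for the difference. How little a non-significant result would tell depends on assumed rates and an assumed level. At two-sided 0.10, unpaired, power runs from 14% (a doubling from 4.2%) through 29% (a tripling) and 37% to 39% (the plan's pairs, Fisher) to about 50% (four- to five-fold rises). Every figure is lower at 0.05. The 4.2% rate comes from longer treatment in other populations, and the rate in glioma patients over one week could be higher or lower. This is an analysis choice worth correcting before the data are read. It does not call the design or the by-dose tabulation into question.

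**What to change.** In section 13.1, for serious events:
- Replace the between-dose test with the within-patient risk difference, 300 minus 75 mg and 300 minus 150 mg, each with a one-sided 95% upper limit from a named method for paired proportions.
- Compute it over the equal 7-day titration windows, in patients who received both doses.
- Report beside it the by-dose proportions in all treated patients, including those who stopped or did not escalate because of toxicity. Show events from the fixed-dose phase separately.
- Name the events that count as serious for this hypothesis.
- State that a non-significant dose comparison is not evidence of no increase, and report the largest increase that the data leave open.

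The cost is wording in the analysis section, with no extra patients or visits. The conclusion becomes an interval, probably a wide one, instead of a yes or no. The paired set leaves out patients who did not escalate, which is why the all-treated proportions must be shown with it.
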